#### Analysis Variables

##### Primary analysis variable:

- Aneurysm rupture (i.e. aneurysmal subarachnoid hemorrhage, SAH) or growth (increase in any aneurysm diameter by  $\geq 1$ mm) on serial imaging (either two MR or CT angiographies) within 36 +/- 6 months from randomization.

##### Secondary analysis variables:

- Any growth or rupture of aneurysm during follow-up irrespective of the duration of trial participation
- Difference of aneurysm volume (defined as increase of aneurysm volume in computerized measurements from source images by  $>10\%$  and  $>3\text{mm}^3$  or aneurysm shape (e.g. development of daughter sac)
- Development of de novo aneurysm on serial imaging.
- If a second aneurysm exists at baseline, this aneurysm will be defined for its localization and analyzed for growth in diameter, growth in volume, and alteration of shape.
- Clipping/coiling during the study period
- Any ischemic or haemorrhagic stroke, defined as clinical symptoms of stroke AND a compatible lesion on imaging
- Myocardial infarction defined as increase of Troponin, CKMB and/or presence of new significant Q waves obtained in ECG
- Vascular death (including fatal stroke, fatal myocardial infarction, sudden death)
- Death from all other causes
- Major spontaneous bleeding requiring hospitalisation defined as substantially disabling bleeding, intraocular bleeding leading to the loss of vision, or bleeding necessitating the transfusion of at least 2 units of erythrocyte concentrates achieved
- Blood pressure; any data on blood pressure management used
- Safety aspects (adverse and serious adverse events, including those mentioned above)
- Quality of life

### 9.2 Definition of Trial Population to be analysed

The primary analysis will be performed for the full analysis set which comprises all patients randomised into the trial. In this set, every patient is analysed according to the group randomised into. Exceptions to this rule can be made for patients for whom non-eligibility became apparent after randomisation, provided all three of the following conditions hold:

- The entry criterion was measured prior to randomisation;
- The detection of the relevant eligibility violations can be made completely objectively;
- All subjects receive equal scrutiny for eligibility violations; (This may be difficult to ensure in an open-label study, or even in a double-blind study if the data are unblinded prior to this scrutiny, emphasising the importance of the blind review.)

The safety set will comprise all patients who have received study medication at least once, and will allocate the patients to the treatment they actually received, regardless of randomisation.

For definition of “premature withdrawal”, “screening failure” and “drop-out” see 4.6.1.

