## PROTOCOL SYNOPSIS

|   |   |
|---|---|
| TITLE                                | Prospective Randomised Open-label Trial to Evaluate risk faCTOR management in patients with Unruptured intracranial aneurysms.  |
| SHORT TITLE                          | PROTECT-U   |
| CLINICAL TRIAL CODE                  | PROTECT-U   |
| EUDRACT NO.                          | 2017-000514-35  |
| INDICATION                           | Intradural saccular unruptured aneurysm   |
| OBJECTIVES                           | The primary aim of this study is to assess the hypothesis that a strategy with low-dose ASA (81-100mg/day) and intensive blood pressure treatment (targeted systolic blood pressure below 120mmHg) with weekly measurements using a home blood pressure measuring device reduces the risk of aneurysm rupture or growth compared with standard care (i.e. no ASA, blood pressure management according to guidelines which usually advise treatment if systolic blood pressure exceeds 140mmHg, and no home device for weekly blood pressure measurements).  |
| PHASE                                | III   |
| INVESTIGATIONAL MEDICINAL PRODUCT(S) | Acetylsalicylic acid (ASA), 81-100mg once per day   |
| STUDY DESIGN                         | Multinational, phase III multicenter, randomised, controlled trial with a PROBE design (prospective, randomised, open-label trial with blinded outcome assessment)  |
| STUDY POPULATION                     | 
Inclusion Criteria
 
 
• Patient with at least one intradural, saccular unruptured aneurysm in whom it is decided not to intervene with preventive neurosurgical or endovascular aneurysm repair and who are monitored on a regular basis for aneurysm growth
 
• 18 years or older
 
• Last aneurysm imaging with either CTA/MRA within the last 3 months
 
• Ability of subject to understand character and individual consequences of clinical trial
 
• Not legally incapacitated
 
• Written informed consent (must be available before enrolment in the trial)
 
 |

|                       |   |
|-----------------------|---|
|                       | 
 
For women with childbearing potential adequate contraception
 
  |

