## 5 INVESTIGATIONAL MEDICINAL PRODUCT (IMP)

### 5.1 Study medication

#### 5.1.1 General Information

The sponsor (UMM) will provide the quantity of trial medication required for the clinical trial sites in Germany and the Netherlands.

Supply of IMP in additional countries will be managed by the national coordinators in accordance with the national regulations.

The medication provided must be used only in the context of this clinical trial. Careful records will be kept of the trial medication supplied to the centres and distributed to the patients. If deficiencies of the trial medication are noticed, the monitor and the project manager must be informed immediately.

Blood pressure lowering drugs will not be part of the IMP. The general practitioner will control the blood pressure target and prescribe blood pressure lowering drugs. The general practitioner can decide himself/herself on the type of antihypertensive drug(s) he/she wants to use to decrease the blood pressure.

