### 5.4.2 Dosage Schedule

The study medication is given only to patients who have consented to study participation and who are randomized to the intervention group.

Maximum duration of treatment: 120 months  
Maximum dose allowed: 100mg ASA daily, orally

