#### 5.4.5 Adjustments to dosage of the IMP in the individual trial subject

- A) The use of ASA may be interrupted, if a patient needs surgery during the course of the clinical trial. It will be resumed as soon as possible after surgery.
- B) No changes in IMP dosage are intended or permitted, even in case patients require a higher dose of ASA for other indications. However, if patients are medically required to be treated with higher doses of ASA (e.g. due to cardiovascular event) while being on treatment with the IMP, the treating physician can prescribe ASA as required and the IMP will be stopped for the time in which ASA is prescribed.
- C) For safety data, patients of the intervention group, who received concomitant long-term ASA will be analysed as per protocol, patients of the control group as ITT.

No further adjustments are planned.

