## 5.5 Randomisation

### 5.5.1 Randomisation method

For randomisation an online tool (<https://www.randomizer.at/>) will be used. Any patient included will be 1:1 randomised into one of the two study arms: 1) a strategy with ASA 81 - 100mg/day and intensive blood pressure treatment (targeted systolic blood pressure below 120mmHg) with weekly measurements using a home blood pressure measuring device; or 2) standard of care.

There is no placebo group. Each study centre will be provided with an access code to perform the randomisation independently. Stratification will occur according to centre.

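### The safety set in Section 9.2 holds no control patient treated as assigned, so it cannot serve the safety comparison and conflicts with Sections 5.4.5 C and 9.3

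*Protocol*

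**What the plan says.** Section 9.2 (Definition of Trial Population to be analysed) names two populations. The full analysis set is all randomised patients, analysed as randomised, with a narrow exception for ineligibility found later. The second population is fixed as follows: "The safety set will comprise all patients who have received study medication at least once". The same sentence adds that the set "will allocate the patients to the treatment they actually received, regardless of randomisation".

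Other sections determine who can meet that condition:

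- The synopsis lists the investigational product as "Acetylsalicylic acid (ASA), 81-100mg once per day", and Section 5.1.2 names no other study medication.
- Section 5.4.2: "The study medication is given only to patients who have consented to study participation and who are randomized to the intervention group".
- Section 5.5.1: "There is no placebo group".
- Section 5.1.1: "Blood pressure lowering drugs will not be part of the IMP".

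Two further places bear on the safety population. Section 5.4.5 C gives this rule for the safety analysis: "patients of the intervention group, who received concomitant long-term ASA will be analysed as per protocol, patients of the control group as ITT". The closing part of Section 9.3 says that the analyses take in every randomised subject, as a full intention-to-treat analysis.

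**The concern.** A safety set defined by at least one dose is usual where every arm receives a study product. Here one arm receives none, so the dosing condition separates the arms instead of removing a few untreated patients from each.

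The intervention also has two components, and the definition follows only one of them. A patient who was treated to the intensive blood pressure target but never took an ASA tablet was exposed to the strategy, yet falls outside the set. Harms of the blood pressure component in such patients would not be counted there.

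At stake is secondary objective D in Section 2.2, which asks whether side effects cancel the benefit of the intervention. That question needs a comparator. A statistician who tabulated adverse events in the population called the safety set would have no control group. One who followed Section 9.3 would have both arms. The protocol should not leave room for both outcomes.

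**Working it through.** **Size of the set under the definition as written**

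1. Planned enrolment (Section 4.1): 776, allocated 1:1. 776 / 2 = 388 per arm, which matches the figure stated there.
2. Control patients treated as assigned who receive study medication: 0. Section 5.4.2 limits it to the intervention arm, and Section 5.5.1 excludes a placebo. Antihypertensive drugs do not count (Section 5.1.1).
3. Intervention patients in the set: 388 − k, where k is the number who never take ASA. The protocol gives no value for k. The largest possible count is 388, at k = 0.
4. Safety set: at most 388 versus 0, which is 388 / 776 = 50% of those randomised. The control count does not depend on k.

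**Could a control patient enter by another route?**

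- A control patient given trial ASA in error would enter, but the as-treated clause would count that patient as treated.
- A control patient prescribed ASA outside the trial has not received study medication, because Section 5.4.5 B separates prescribed ASA from the investigational product. Even on a looser reading, the patient would be grouped with those on ASA.

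Neither route produces a comparator.

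**The definition against its own second clause**

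Allocating patients to the treatment received presupposes at least two groups. With two components there are 2 × 2 = 4 possible states: both, ASA only, intensive blood pressure treatment only, and neither. The dosing condition admits only the two states that include ASA. Section 9.2 does not say how those two are to be grouped.

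**The sections side by side**

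| Place | Population implied for safety |
|---|---|
| 9.2, safety set | Patients with at least one dose of study medication: ≤388 vs 0 |
| 5.4.5 C | On concomitant long-term ASA: intervention patients per protocol, control patients by ITT |
| 9.3, closing part | All randomised: 388 vs 388 |

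These do not agree. Section 5.4.5 C also refers to a per-protocol analysis, although Section 9.2 defines no per-protocol set.

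**Are comparative safety data available?**

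Yes. Section 8.2 starts adverse event observation at randomisation, not at first dose. Section 6.3 gives both arms the same visit schedule for data collection. Stroke, myocardial infarction, death, major bleeding and adverse events are listed secondary endpoints in Section 2.2, and they recur in the analysis variables under Section 9.1.

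**The case against.** The strongest reply is that nothing in the protocol is tied to the safety set. The term occurs only in Section 9.2, and no endpoint is assigned to it. Section 9.3 says that outcome events will be compared between the two groups and that all randomised subjects are analysed. A reader might infer that no between-arm safety comparison is possible, or that the plan can yield only one-arm counts of harms. The documents do not support that: the full analysis set has safety data for both arms. This part of the reply stands.

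A reader might also take the serious adverse events related to the intervention in the cited blood pressure trial (4.7% versus 2.5%, Section 1.3) as a contrast that this plan forfeits. That is not supported either. Section 8.1.6 assesses causality against the investigational product, so that particular contrast is not what this trial records under any safety set, and comparison of all serious events remains possible in the full analysis set.

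Nor is bias shown from Section 5.4.5 C. One reading is that an intervention patient switched to prescribed ASA still counts as treated, while a control patient on ASA stays in the control arm. Both would then remain in their randomised arms. The sentence is ambiguous, and its different terms for the two arms need clearing up, but it cannot be called biased as it stands. For control patients on long-term ASA, "patients of the control group as ITT" in fact keeps them in the safety data.

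It can further be said that the wording looks like a template, that its intent is plain, and that Section 9.3 defers final details to the SAP. This part does not stand. The protocol does not leave the safety population open; it states one that does not fit the design. An SAP that follows it inherits the error, and one that departs from it contradicts the protocol.

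Finally, as-treated grouping is a legitimate choice, and replacing it with grouping by randomised arm is partly a matter of preference. This is accepted. The definition must supply a control group, whichever grouping is chosen.

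**Conclusion.** The point holds in a limited form. As worded, the safety set contains at most 388 intervention patients and no control patient treated as assigned. It also omits intervention patients who took up only the blood pressure component; the protocol gives no figure for how many. It cannot support the comparison that objective D requires, and it conflicts with Sections 5.4.5 C and 9.3.

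The effect is confined to that set. Safety data exist for both arms, a comparison in all randomised patients remains open under Section 9.3, and the primary analysis is untouched. The count assumes planned enrolment and that study medication means the investigational product. The SAP is not at hand and may refine the definition, but the protocol sentence is wrong for a design without placebo and should be corrected.

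**What to change.** In Section 9.2, redefine the safety set in one of two ways:

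- all randomised patients (planned 388 versus 388); or
- all control patients plus intervention patients who started either component of the intervention.

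State the grouping rule in the same paragraph so that a control group exists. Grouping by randomised arm fits objective D, which concerns the strategy as a whole. If as-treated grouping is kept, say how patients who received only one component are classed.

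Replace the analysis rule in Section 5.4.5 C with a single rule for concomitant long-term ASA that applies in both arms. Either define the per-protocol set it mentions or drop the term. Then align both places with the statement in Section 9.3 on who is analysed. An analysis by ASA exposure can be added as an optional sensitivity analysis.

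The cost is one paragraph in Section 9.2, one line in Section 5.4.5 and a check of Section 9.3. No new data are needed, because adverse events are already collected in both arms. As the trial is open-label, the change should be made before the data are examined and carried into the SAP, which under Section 9.3 must be authorised before the database is opened.

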### 2.2 Secondary Objectives and Secondary Endpoints

Secondary objectives of the study are:

- A) To assess whether ASA reduces the risk of aneurysm rupture or growth compared with no ASA treatment.
- B) To assess whether intensive blood pressure lowering therapy reduces the risk of aneurysm rupture or growth compared with no intensive blood pressure lowering therapy.

- C) To assess whether intensive blood pressure treatment plus ASA reduces the incidence of cardiovascular events compared with standard BP treatment alone.
- D) To assess whether beneficial effects of the intervention with intensive blood pressure treatment and ASA are not negated by side effects of the intervention.
- E) To assess the effect of the intervention on quality of life
- F) To investigate if the intervention is cost-effective

Secondary endpoints of the study are:

1. Any growth or rupture of aneurysm during follow-up irrespective of the duration of trial participation
2. Difference of aneurysm volume (defined as increase of aneurysm volume in computerized measurements from source images by >10% and >3mm^3) or aneurysm shape (e.g. development of daughter sac)
3. Development of de novo aneurysm on serial imaging
4. If a second aneurysm is present: Growth in diameter or volume and alteration of shape of this second aneurysm.
5. Clipping/coiling during the study period
6. Any ischemic or haemorrhagic stroke, defined as clinical symptoms of stroke AND a compatible lesion on imaging
7. Myocardial infarction defined as increase of Troponin, CKMB and/or presence of new significant Q waves obtained in ECG
8. Vascular death (including fatal stroke, fatal myocardial infarction, sudden death)
9. Death from all other causes
10. Major spontaneous bleeding requiring hospitalisation defined as substantially disabling bleeding, intraocular bleeding leading to the loss of vision, or bleeding necessitating the transfusion of at least 2 units of erythrocyte concentrates
11. Blood pressure; any data on blood pressure management used
12. Safety aspects (adverse and serious adverse events, including those mentioned above, see also 8.1.6 and 8.2)
13. Quality of life (as determined by completion of the paper-based EQ-5D-5L form by patient)

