#### 5.1.2 Characterisation of study medication

The study medication is:

|  |   |
|--|---|
| International Nonproprietary Name (INN): | Acetylsalicylic acid                              |
| ATC code:                                | B01AC06   |
| Pharmaceutical formulation:              | Tablets   |
| Dose                                     | Daily, 81 – 100 mg (depending on country)         |
| Mode of administration:                  | Oral  |
| Storage instructions:                    | Store below 30°C / 86° F, protected from humidity |

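### The safety set in section 9.2 admits only patients who took study medication, so as written it contains no control patients and contradicts its own grouping rule and other sections

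*Protocol*

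**What the plan says.** Section 9.2 defines two populations. The full analysis set is all randomised patients, with narrow exceptions for ineligibility found later. For the safety set the text is "The safety set will comprise all patients who have received study medication at least once", and the same sentence goes on to say that the set "will allocate the patients to the treatment they actually received, regardless of randomisation".

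What counts as study medication is fixed elsewhere in the protocol:

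- 5.1.2 gives its name as "Acetylsalicylic acid".
- 5.1.1 says "Blood pressure lowering drugs will not be part of the IMP".
- 5.4.2 says "The study medication is given only to patients who have consented to study participation and who are randomized to the intervention group".
- 5.5.1 says "There is no placebo group".

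Three other places treat control safety data as something to be analysed:

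- 5.4.5(C), on safety data and long-term concomitant ASA, has "patients of the control group as ITT".
- 8.2 starts adverse event observation at randomisation, not at first dose.
- The closing part of 9.3 (printed under the budget impact heading) includes every randomised subject in the analyses.

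**The concern.** The entry rule in 9.2 suits a placebo-controlled drug trial, where each arm receives something that counts as study medication. Here only one arm does, so an open-label control patient on standard care cannot qualify. The randomised intervention also has two components, and the rule recognises only one of them. An intervention patient whose blood pressure treatment is intensified but who never takes an ASA tablet is left out.

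The stake is the reading of harm. Objective D in 2.2 is "To assess whether beneficial effects of the intervention with intensive blood pressure treatment and ASA are not negated by side effects of the intervention", and adverse and serious adverse events are secondary endpoint 12. A side-effect rate in one arm says little about what the intervention caused. If the analyst follows 9.2 to the letter, the one set named for safety can only describe the intervention arm. If the analyst follows 9.3 or 5.4.5(C), the population is a different one. In an open-label trial that choice should be settled before the data are examined.

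**Working it through.** **Step 1: planned arm size.** Section 9.1 gives 353 per group and a 10% dropout allowance. 2 × 353 × 1.10 = 776.6, stated as 776. With 1:1 allocation, 776 / 2 = 388 per arm, which matches section 4.1. The sample size is not in dispute; it only supplies the denominator.

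**Step 2: apply the entry rule.** Entry requires at least one intake of study medication.

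| Group | Gets study medication? | Source | In the safety set as written |
|---|---|---|---|
| Control, 388 | No ASA supplied, no placebo | 5.4.2, 5.5.1 | 0 |
| Intervention, took ASA at least once | Yes | 5.4.2 | Yes |
| Intervention, blood pressure component only | No; antihypertensives are not study medication | 5.1.1 | No |

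The total is therefore at most 388 + 0 = 388, against 388 + 388 = 776 if all randomised patients were included. A control patient given trial ASA by mistake would enter the set, but the as-treated clause would then place that patient with the ASA-treated. The control group stays empty either way.

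The documents give no figure for intervention patients who never take a tablet. Each 1% of the arm would be 0.01 × 388 = 3.9 patients. The conclusion does not depend on that share.

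**Step 3: set the passages side by side.**

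- *9.2, first half against second half.* Allocating patients by treatment received presupposes at least two treatment groups. The entry rule leaves one.
- *9.2 against 5.4.5(C).* The latter has control patients' safety data analysed by intention to treat. Its context is long-term ASA use, so it is not a general rule, but it cannot be carried out on a set without controls.
- *9.2 against 8.2.* Events are observed from randomisation in everyone, yet the set is defined by first dose.
- *9.2 against the end of 9.3.* All randomised subjects are to be analysed, with no carve-out for safety.

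**Step 4: why a one-arm rate is not enough.** Section 1.3 reports intervention-related serious adverse events of 4.7% with intensive and 2.5% with standard blood pressure treatment in the cited cardiovascular trial. 2.5 / 4.7 = 0.53, so about half of the intensive-arm rate was also seen with standard treatment. For transfused gastrointestinal bleeding in the cited trial of ASA in women, the relative risk was 1.40, and 1 / 1.40 = 0.71. These are other populations and serve only as illustration: without controls, background events cannot be separated from harm.

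**The case against.** The strongest reply is that little is lost in practice. Visit schedules are the same in both arms (6.3), adverse events are asked about in all participants, and all serious events are evaluated during the study and for the final report (8.2). Stroke, myocardial infarction, death, major bleeding and adverse events are listed as secondary variables (9.1), and 9.3 compares outcome events between the two groups by risk ratio. The term safety set occurs only in 9.2, and no section assigns objective D or endpoint 12 to it. The as-treated clause suggests that the authors meant to include controls.

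Most of this stands, and it limits the point. A reader might infer that the trial cannot compare safety between arms at all, or that harms of blood pressure lowering in patients who never took ASA go uncounted. The documents support neither reading: the data are collected in both arms, and all randomised patients can be compared. That objective D must be run on this set is likewise an inference.

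The reply does not rescue the definition. It is the only population the protocol names for safety, and its terms leave the control group empty. That another set could be used shows that the sections disagree; it does not say which one governs. Nor can this be left to a statistical analysis plan as detail. The protocol states the rule explicitly, so a plan that follows it repeats the error and a plan that departs from it contradicts the protocol.

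**Conclusion.** The safety set definition is wrong as written. It holds 0 of 388 planned control patients (apart from any given trial ASA in error) and at most 388 intervention patients, and it omits those who received only the blood pressure component. It conflicts with its own grouping clause, 5.4.5(C), 8.2 and the end of 9.3. The count rests on the protocol's own definition of study medication and its planned allocation, with no outside figure.

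The consequence is confined to this set: a between-arm safety comparison cannot be made on it, but can still be made on all randomised patients. The primary analysis is not affected.

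**What to change.** Replace the safety-set sentence in 9.2 with wording such as: *The safety set comprises all randomised patients in both arms, including intervention patients who never took ASA. The main safety comparison is by randomised arm. A supportive analysis groups patients by actual ASA intake.*

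If the sponsor prefers as-treated grouping for the main analysis, that also works, provided the rule says that patients without ASA intake form the comparator and where intervention patients without ASA belong. Intensified blood pressure treatment should not be used as the exposure criterion unless it is defined. Controls receive guideline-based blood pressure care, and 9.3 expects intensive-treatment data from both arms, so a control whose treatment is stepped up could be counted as intervention-exposed.

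5.4.5(C) and the closing part of 9.3 should be reconciled with the new sentence, so that one population and one grouping rule govern safety. The cost is one changed sentence, those two cross-checks, and the same wording in the statistical analysis plan. No new data are needed, because adverse events are already recorded from randomisation in both arms.
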